## B2e: Clinic Visits

**B2ei. Orientation meeting.** Subjects will attend an orientation meeting to be further informed about the study, to obtain consent, and to determine eligibility. Once determined to be eligible, subjects will provide a spot urine sample for nicotine levels, and then they will be scheduled for a clinic visits and will keep a daily diary to monitor their ST intake (time of dip onset and time when dip was expectorated). We have used daily diaries with ST users for up to a period of 8 weeks with good compliance.

**B2eii. Clinic visit.** At the clinic visit, subjects will be asked to complete questionnaires on demographic and tobacco use history, on ST dependence, on psychiatric, medical and alcohol use history, and on factors that might moderate the extent of tobacco exposure. Subjects will also be asked to complete a series of questionnaires during each of the orientation and clinic visits. These questionnaires will assess for tobacco use status and any factors that might confound our biomarker measures. These factors include exposure to environmental tobacco smoke, dietary intake, level of physical activity, medical status (e.g., infections), alcohol intake prior to visit and use of any other nicotine containing products. First morning urine sample will be collected to measure carcinogen biomarkers. Two spot urines (one at orientation and one at the clinic visit) total nicotine equivalents and nicotine metabolite ratio. Vital sign measurements and CO will be obtained and at the U of MN site, blood samples taken (23 ml of blood obtained by a nurse). In addition, subjects will provide us with at least 3 samples (usual size dips) of their smokeless tobacco product at each of the two visits. Each of these dips will be weighed to obtain an estimate of the mean weight per dip. Clinic visits will be scheduled on Tuesdays, Wednesdays or Thursdays. At each site, tins of unused ST will be obtained from a random sample of 10 subjects from each of the 6 brands of ST and sent to CDC for toxicant

analysis. At the end of the study, all subjects will be encouraged to quit ST use. Cessation materials and referrals will be provided to all participants at the conclusion of the second visit.

#### ***B2f. Subject payments.***

Subjects will be paid \$100 for participation, \$25 for the Orientation and \$75 for the clinic visit.

#### ***B2g. Adherence to protocol procedures and data integrity.***

Standard operating procedures will be developed. Face-to face training for research personnel will occur prior to the study, where the protocol and procedures will be carefully described. Case report books will be made for the different sites to maximize parallel recording of data. Each visit will have a checklist of all the measures that need to be taken and the order by which these measures are administered.

Weekly conference calls will occur among the research coordinators to trouble shoot and to make sure that all protocol procedures are followed. On a once a month basis, the PI and co-investigators will participate in this conference call. During these conference calls, the number of subjects enrolled, the data collection process, the results from data monitoring and other issues of concern will be discussed. As another measure to ensure data collection integrity, the project manager from the University of Minnesota will make a visit to the various sites after they have enrolled 10 subjects to make sure that the protocol is being followed carefully and all the data is being collected properly. Another on site visit will occur 3 months from the initiation of the study. An additional visit will be made in Year 1 if necessary, and 2 visits in Year 2.

Human subject consent forms, pen and paper and electronic subjective forms, and containers for the urine biosamples and for ST collections will be given bar codes individualized for each subject. Each site will receive a separate box for each subject, packaged at the University of Minnesota, that contains the bar coded paper and pencil subjective forms and collection containers. Most of the subjective measures will be administered via computer in electronic forms on a secured website. Subject numbers, represented on the bar codes, will be entered into the computer prior to subject data entry. Forms will include programming features to ensure valid data (i.e., input masks, validation criteria, skipout logic) and data will be exported to Microsoft Excel files that are de-identified of any personal health identifiers. All other data not captured directly in the website at the other sites (e.g., pencil-and-paper forms) will be sent to the University of Minnesota on a weekly basis (with photocopies of originals maintained at the other sites). A data monitor will be available at the University of Minnesota site and irregularities (e.g., wrong date on the forms, inconsistent data) or missing data will be flagged by the monitor and sent to the site for comment or correction to ensure the integrity of the data.

All de-identified biosamples will be sent to the University of Minnesota on a monthly basis after both biosamples have been collected for each subject. A list of subject number and biosamples sent will be recorded by each site and when the samples are received, the researcher at the University of Minnesota will note each subject number and biosample that was received. The samples-received list will be posted on a secure website so that each site can check it against the samples-sent list.

### **C. Statistical analyses**

#### **C1. Analytic Approach**

##### ***Primary Aims***

1. To determine the toxicant exposure associated with currently marketed oral tobacco products with varying levels of toxicants and nicotine.

Subject characteristics will be examined across sites and ST users at each site will be compared to the characteristics of the respective state population of ST users. The outcomes for this study are the uptake of toxicants, as measured by biomarkers of exposure including NNAL, NNN, nitrosoamino acids,

1-HOP and total nicotine equivalents and biomarkers of effect such as CVD risk factors. The distribution of each biomarker will be examined to determine if a data transformation is necessary. From our previous experience, the distributions of many biomarkers are often skewed with a long right tail and need to be analyzed in the natural log scale. The two biomarker assessments for nicotine from each subject will be used to evaluate the reliability, as measured by the intraclass correlation. The two readings will then be averaged for the subsequent analysis. The geometric mean and the corresponding 95% confidence interval for the biomarkers will be calculated for each brand. The one-way analysis of variance (ANOVA) will be used to compare the mean toxicant levels between all six brands. If this global test is significant, then the Tukey's studentized range procedure will be used for pair-wise comparisons between brands, while maintaining an overall significance level of 5%.

2. To determine if toxicant and nicotine exposure is related to product factors such as the levels of these constituents (nicotine, NNK and NNN) in the products and patterns of use such as tins per week, dips per day, duration per dip, total dip duration (dip per day x duration per dip), weight per dip.

Pearson or Spearman correlations will assess the relationship between toxicant and nicotine exposure and the level of toxicants in the tobacco products. Furthermore, regression models will determine the degree of association between exposure and patterns of use, while controlling for the different ST brands. Specifically, total nicotine equivalents will be correlated with the free nicotine levels of the products and patterns of use; NNAL will be correlated with the NNK levels of the product and patterns of use; NNN exposure will be correlated with the amount of NNN in the product and patterns of use; and 1-HOP exposure will be correlated with the amount of pyrene and patterns of use.

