### **B2. Procedures**

*Subject recruitment.* Subjects (N=600) will be recruited from a) Minneapolis/St. Paul, MN, b) Eugene, OR, and c) Morgantown, WV. Each site will recruit 200 subjects over the course of 2 years, with a total of 100 subjects recruited for each brand that is listed in Table 2. We anticipate no problems with recruitment. Surveys conducted in 2007 or 2006 estimated Minnesota and Oregon male ST prevalence of 6.0% and 6.5%, respectively. The 2006 West Virginia Adult Tobacco Survey estimated the male ST prevalence to be about 16%. Multiple avenues of recruitment will be pursued to ensure as representative of a sample as possible. These methods include radio, cable, newspapers (want ads and display ads), restroom stall ads, sporting good stores, WIC clinics, internet and press releases. The recruitment advertisements will state that daily ST users are needed for a study that examines the effects from ST use; blood (only at U of MN site), oral cells (only at U of MN site) and urine samples will be obtained. It will further state that subjects will be paid for participation. Potential adult subjects will be asked to call the research clinic number where the study will be explained, brief phone screening will be conducted, and interested and potentially eligible subjects will be asked to attend an orientation meeting. The brands of ST will not be listed on the advertisements to ensure that we are recruiting actual users of the brands rather than subjects who falsely claim using one of the brands of interest in order to obtain money for study participation. Subjects will be informed that the study determines the extent of exposure to toxicants and the effects of these exposures across different brands of ST.

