### **B2b. Measures and Schedule of Administration**

The following provides the measures that will be administered. Table 1 describes the measures to be obtained and the timing of the measurement. The majority of these measures have been used in our prior studies and have been found to be dose-sensitive to change in amount of smoking or ST use, or sensitive to switching products (e.g., conventional cigarettes to modified cigarettes, cigarettes to ST products).

Table 1. Schedule of visits and measures Study 1

	Visit	
	Orientation	1
Consent	X	
Baseline and Moderator Measures		
Demographics	X	
Medical History and Concomitant meds	X	X
Tobacco Use History and Exposure,	X (brief)	
Severson ST Dependency Scale	X	
Perceived Health Risk	X	X
Stages of Change		X
CES-D		X
PANAS		X
Perceived Stress Scale		X
Michigan Alcohol Screening Test,		X
NIAAA Alcohol Use Questionnaire		
Exposure and Lifestyle Measures		
Occupational Health History		X
ETS and Social Influences		X
Dietary – consumption of meats		X
IPAQ		X
Medical status (e.g., infections)		X

Novel Determinants and Measures of Smokeless Tobacco Use: Study 1

Daily Tobacco Use Diary	X (start at screen)	X
Vitals (Blood pressure and heart rate)		X
Weight		X
Concomitant Medications		X
Carcinogen Exposure Urinary total NNAL Total NNN Nitrosoamino acids NPRO and MNPA Phenanthrene tetraol 1-hydroxypyrene (1HOP)		X
Cardiovascular Measures (UMN only) Lipoproteins C-reactive protein Fibrinogen WBC		X X X X
 Buccal assay		X
 Nicotine and metabolites	X	X
 Product Constituent Testing		X
 Weight per dip	X	X
Carbon Monoxide		X

Buccal assays to be placed in biorepository for future analyses (UMN only)

Urinary total nicotine equivalents and nicotine metabolite ratio (3-HC:cotinine)

Product constituent testing will be conducted on a random sample of 30 tins for each brand of ST (10 brands from each site)

Estimated weight per dip will be calculated by averaging the weight of 3 typical daps

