6) Cardiovascular Disease (CVD) Risk Factors. We will collect samples to measure CVD risk factors only at the Minnesota site to save costs. CVD risk factors will be analyzed at the University or Minnesota Medical Center Fairview, Collaborative Studies Clinical Laboratory, Minneapolis, MN. To date, most of the existing studies on CVD risk factors in ST users have been conducted in Sweden. A review of these studies shows that exclusive ST users do not demonstrate higher CVD risk factors (e.g., lipoproteins, biomarkers of oxidative stress and inflammation, endothelial function and platelet activation, carotid intima media thickness) compared to non-users among Swedish ST users and similar results have been observed with healthy young US snuff users [126, 138]. On the other hand, a few studies conducted with ST users in India have shown elevation in lipoproteins and triglycerides [139, 140]. Because of the limited knowledge of US products and a meta-analyses that shows an increased risk in CVD and stroke observed in the US population of smokeless tobacco users (although not the Swedish population [33] with the exception of fatal cardiovascular disease [128, 141]), the following CVD risk factors, which have been predominantly observed to be increased in cigarette smokers, will be assessed in our study: a) Lipoproteins, such as total plasma cholesterol, high and low density lipoproteins (HDL and LDL, respectively), and triglycerides. These markers were found to be dose-sensitive to cigarette exposure in our prior studies. Subjects will fast for 10 hours prior to blood draws. Preferably sampling will be done in early morning, but samples can be done mid-day according to work schedules of subjects as long as the subjects are fasting. b) C-reactive protein is considered to be an inflammatory marker or mediator and its release by the liver is stimulated by pro-inflammatory cytokines, including interleukin 6 (IL-6). Increases in C-reactive protein have been predictive of future vascular events and course of pre-existing vascular disease, and smoking has been found to modulate levels of this protein [e.g., 142, 143]. Several mechanisms by which C-reactive protein contributes to the risks of cardiac disease have been described [143, 144]. c) Fibrinogen is a marker for thrombosis

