and is a glycoprotein involved in the coagulation response to vascular and tissue injury. Fibrinogen is also considered to contribute to vascular disease in other ways besides its role in thrombosis such as stimulating smooth muscle cell proliferation, promoting platelet aggregation and increasing blood viscosity [145]. Elevated fibrinogen levels have been found to be strongly predictive of cardiovascular morbidity and mortality [143]. Prior studies have shown a dose-response relationship between fibrinogen levels and number of cigarettes smoked [146]. d) White blood count, also an inflammatory marker, has been found to be higher in smokers than non-smokers [147, 148] and associated with cardiovascular disease [142] and in our studies was observed to be the most dose-related marker for cigarette reduction [84].

7) Buccal cells biomarkers. Although the grant proposal will not be able to bear the cost for analyses of buccal biomarkers, we will be collecting buccal cell samples to be placed in a biorepository with the hopes of obtaining future funding for their analysis. Buccal cells will be obtained through two methods (oral cheek swab and mouth wash for DNA extraction). These buccal cells will be frozen, stored and labeled in accordance to the procedures used in our NCI contract (N01-PC-64402) and will be made available to investigators associated with the contract or outside of this contract upon review of their proposal and approval from their respective IRBs. All samples will be de-identified. Examples of potential biomarkers include cellular autofluorescence (a method being tested by [name] at Roswell Park Cancer Institute), mitochondrial mutations in oral cavity cells (an analyses being tested by [name] at Georgetown University) and nf Kappa B p65 staining (an analyses conducted for NCI contract N01- CN-15000 by [name] at the University of Minnesota).

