### ***B2d. Tobacco Products***

For Study 1, usual brand of ST products will be used. We chose products that had substantial market share and showed a range in nicotine level and in NNK and NNN levels [4, 46, 75, 151]. Table 2 shows the brands that were chosen for testing. Free/unprotonated nicotine levels were considered high (H) if they were > 5 mg/g, medium (M) if they were between 2-5 mg/g and low if they were < 2 mg/g [3]. TSNA levels were based on a classification that was developed by [name] ([name], report for WHO, TobReg). High (H) levels were NNN plus NNK > than 10 µg/g, Medium (M) levels were NNN plus NNK from 2-10 µg/g, and Low (L) levels were NNN plus NNK < 2 µg/g. Products that are in the Low range for both nicotine and TSNAs tend not be manufactured.

Table 2

Group	Product	Test Date	# Tins/ Regions	Nicotine (mg/g wet)	NNK+NNN (µg/g wet)	Nicotine Group	TSNA Group
1	Camel Snus (All Flavors)	Fall 2010		2.65		Low	Low
	Marlboro Snus (All Flavors)						
	Skoal Long Cut Mint	Fall 2011	3 / 2	1.2	1.23		
	Skoal Fine Cut Original	Spring 2011	1 / 1	2.79	1.88		
2	Copenhagen Long Cut Original	Fall 2010	1 / 1	3.51	2.55	Med	Med
	Kodiak Wintergreen	Spring 2010	9 / 3	4.51	2.73		
	Skoal Bandits Wintergreen	Spring 2010	11 / 3	3.05	3.72		
	Skoal Pouches Straight	Spring 2011	1 / 1	4.02	2.58		
	Skoal Pouches Wintergreen	Spring 2011	1 / 1	3.89	2.81		
	Grizzly Long Cut Straight	Spring 2010	5 / 2	4.23	3.84		
	Skoal Long Cut Straight	Spring 2010	9 / 3	3.15	3.11		
3	Grizzly Long Cut Mint	2010 summary		7.58	3.72	High	Med
	Grizzly Long Cut Wintergreen	Spring 2010	4 / 2	5.12	3.05		
	Grizzly Pouches Wintergreen	Spring 2011	1 / 1	6.25	3.71		
	Skoal Pouches Mint	Spring 2011	1 / 1	5.19	2.15		
	Kodiak Pouches Wintergreen	Spring 2011	1 / 1	5.88	3.44		
4	Grizzly Fine Cut Regular	Spring 2011	1 / 1	4.41	15.3	Med	High
6	Kodiak Long Cut Mint	Spring 2011	1 / 1	3.9	1.91	Med	Low
	Kodiak Long Cut Straight	Spring 2011	1 / 1	4.06	1.88		
8	Copenhagen Fine Cut Original	Spring 2010	9 / 3	2.43	3.45	Low	Med
	Copenhagen Long Cut Straight	2010 summary		2.56	2.07		
	Grizzly Pouches Straight	Spring 2011	1 / 1	0.48	4.0		
	Skoal Long Cut Classic	Spring 2011	1 / 1	2.88	2.88		
	Skoal Long Cut Wintergreen	Spring 2011	1 / 1	2.7	2.51		

Nicotine Group	mg/g wet weight
Low	<3
Medium	3-5
High	>5

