## **C2. Power Considerations:**

The goal is to enroll 100 subjects for each of the six brands listed in Table 2. The mean toxicant uptake level is expected to vary between brands; however, the standard deviation (SD) should

be similar for all brands. This is the common SD and is equivalent to the root of the Mean Square Error (MSE) from the one-way ANOVA. With a total of 600 subjects, this F-test will have 92% power to detect a significant difference at the 0.05 level if the brands with the largest and smallest means differ by at least one-half the common SD. Therefore, if the common SD for the biomarker was 10 units, then there would be a 92% chance that we find a significant difference between brands if the biggest and smallest means were at least 5 units apart. This analysis was done using Power Analysis and Sample Size (PASS) 2005 by NCSS, Inc.

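### CVD risk factors are listed outcomes under Primary Aim 1 but are measured only in about 200 Minnesota subjects using self-chosen brands, and no covariate-adjusted brand comparison is planned for them

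*Combined protocol and SAP*

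**What the plan says.** The outcome sentence under Primary Aim 1 (C1) names several exposure biomarkers and ends with "1-HOP and total nicotine equivalents and biomarkers of effect such as CVD risk factors". Item 6 of B2bii itemises the CVD factors as lipoproteins, C-reactive protein, fibrinogen and white blood count, and states: "We will collect samples to measure CVD risk factors only at the Minnesota site to save costs". Table 1 in B2b agrees: "Cardiovascular Measures (UMN only) Lipoproteins C-reactive protein Fibrinogen WBC". On numbers, B2 says "Each site will recruit 200 subjects over the course of 2 years", so Minnesota supplies 200 of 600. On how subjects come to be in a brand group, B2d says "For Study 1, usual brand of ST products will be used".

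For analysis, Primary Aim 1 says "The one-way analysis of variance (ANOVA) will be used to compare the mean toxicant levels between all six brands", followed by Tukey's procedure. No covariates are mentioned. Control of confounders appears only under Secondary Aim 3, where the outcomes in parentheses are total nicotine equivalents, total NNAL and total NNN. Aim 2 covers nicotine equivalents, NNAL, NNN and 1-HOP. Neither aim mentions a CVD marker.

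C2 gives one power figure: "With a total of 600 subjects, this F-test will have 92% power to detect a significant difference at the 0.05 level". It is for toxicant uptake, with brand means spanning half the common SD.

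**The concern.** Brand is self-selected, so brand groups may differ in age, sex, medication, diet, activity or drinking. Lipids, C-reactive protein, fibrinogen and white count are not specific to tobacco, so such differences can move them whatever the product does. As C1 stands, a CVD marker either goes through an unadjusted ANOVA or has no stated brand comparison at all, because the ANOVA sentence speaks of toxicant levels. Under both readings there is no adjusted comparison.

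At stake is what the study can report on biomarkers of effect. An unadjusted difference could be credited to a product when it belongs to that product's users. In the other direction, C2 gives no precision for the one-site outcomes, so a non-significant CVD result could be taken as evidence that brands are alike.

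**Working it through.** **1. Is an adjusted CVD comparison stated anywhere?** Taking the aims in C1 in turn:
- Aim 1: one-way ANOVA and Tukey, no covariates.
- Aim 2: correlations and regressions for nicotine equivalents, NNAL, NNN and 1-HOP.
- Aim 3: ANCOVA and regression with confounder control, for nicotine equivalents, NNAL and NNN.
- Aim 4: market-share weighting of the Aim 1 means.

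None gives an adjusted brand comparison of a CVD marker.

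**2. How much could a covariate imbalance matter?** The documents give no figures, so these inputs are assumptions: a covariate correlated r with the marker, covariate means equally spaced over g SD across six brands, no true brand effect, and an even split at Minnesota (n = 200/6 = 33.3 per brand). The spurious span of marker means is w = r × g. For six equally spaced means spanning w, the sum of squared deviations is 0.7w², so the noncentrality is λ = 33.3 × 0.7 × w². The test is F on 5 and 194 df at 0.05.

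| r | g (SD) | w (SD) | λ | Chance of significance |
|---|---|---|---|---|
| 0.3 | 0.5 | 0.15 | 0.53 | 7% |
| 0.3 | 1 | 0.30 | 2.10 | 16% |
| 0.4 | 0.5 | 0.20 | 0.93 | 9% |
| 0.4 | 1 | 0.40 | 3.73 | 27% |

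The nominal rate is 5%.

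**3. Reproducing C2.** Inputs from C2: six brands, 100 each, range 0.5 SD, alpha 0.05. Set SD = 1. Then λ = n × Σ(μᵢ − μ̄)², with 5 and N − 6 df. C2 does not say where the four middle means lie. For equal spacing (±0.25, ±0.15, ±0.05), Σ = 2 × (0.0625 + 0.0225 + 0.0025) = 0.175, so λ = 17.5 and power is 91.6%. This matches 92%, and of the four patterns tried it is the only one within two points.

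**4. The same configurations at N = 200.** This carries the 0.5 SD range over to markers for which C2 did not set it, and keeps the even split.

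| Pattern over 0.5 SD | Σ | λ, N = 600 | Power | λ, N = 200 | Power |
|---|---|---|---|---|---|
| Two extremes, four at midpoint | 0.125 | 12.5 | 78% | 4.17 | 30% |
| Equally spaced | 0.175 | 17.5 | 92% | 5.83 | 41% |
| One brand differs | 0.208 | 20.8 | 96% | 6.94 | 48% |
| Three at each end | 0.375 | 37.5 | over 99% | 12.5 | 77% |

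With equal spacing, 80% power needs a range of 0.43 SD at 600 and 0.75 SD at 200. The smallest difference Tukey can declare significant is q/√n: 4.043/√100 = 0.40 SD and 4.071/√33.3 = 0.71 SD.

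The even split is also an assumption, because B2 sets brand totals across sites only. An illustrative Minnesota split of 60/50/40/25/15/10 gives 23% to 57% for equally spaced means (average 39%), depending on which brands are large.

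**The case against.** The strongest reply is that C2 is not in error. It claims 92% for toxicant uptake in 600 subjects and says nothing about CVD markers, and B2bii openly gives the Minnesota restriction and its reason. This stands. A reader might infer that the plan advertises 92% power for CVD outcomes when the true figure is 41%. The documents support neither half: the 92% is never applied to those markers, and the 41% borrows an effect size set for other outcomes, infers the spacing of means and assumes the brand split.

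It can also be said that safeguards exist. Eligibility excludes current infection, antibiotic use, unstable medical conditions and recent alcohol; blood is drawn after a 10-hour fast; and C1 plans brand-specific 95% confidence intervals, which would show the lower precision. These reduce noise and some acute influences. They do not balance age, sex, long-term medication, diet or activity across brands, so they do not replace adjustment.

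A third reply is that Aim 1 is descriptive and its ANOVA is unadjusted for every biomarker; Aim 3 also leaves out 1-HOP, the nitrosamino acids and phenanthrene tetraol. That is correct, and an unadjusted comparison does describe users as they are. It is why the unadjusted result should be kept. It does not close the gap for markers whose levels depend heavily on things other than tobacco.

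Finally, the correlations and spans used to size the confounding have no source in the documents. They show what is possible, and at the low end the effect is small (7% against 5%).

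**Conclusion.** The point holds as an omission in C1. CVD markers are listed outcomes under Primary Aim 1, brand groups are self-selected, and no adjusted brand comparison is stated for them. That rests on the text alone. The possible distortion is illustrative: 7% to 27% false positives against 5% under the assumed imbalances. The documents do not show that brand groups actually differ on any covariate.

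The power matter is secondary and calls for a clarification in C2. If the 0.5 SD range is carried over and brands are evenly split at Minnesota, power is about 41% with equally spaced means and 30% to 77% across patterns. The 41% should be quoted only with that range. A non-significant CVD result should not be read as no difference. The toxicant comparison in 600 subjects is unaffected.

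**What to change.** **C1, Primary Aim 1.** For each CVD marker, add an ANCOVA comparing brands, adjusted for age, sex and relevant medication (for example lipid-lowering or anti-inflammatory drugs), plus the confounders the protocol already collects: diet, physical activity, alcohol and infection status. Add body weight in a sensitivity model only, because it may partly result from nicotine use. Report adjusted brand differences with 95% confidence intervals beside the unadjusted result.

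**C2.** Add a sentence such as: The 92% applies to toxicant uptake in 600 subjects and not to the CVD markers, which are measured only at Minnesota (about 200 subjects). If the same 0.5 SD range and an even brand split were assumed, their power would be about 41% with equally spaced means (30% to 77% across patterns). A non-significant CVD result will not be read as no difference.

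**Cost.** A few sentences and one extra set of models. The covariates are already collected (B2bi, B2bii and Table 1), so no new subjects, visits or assays are needed. The downside is a less favourable stated power. Adjustment may recover some of it: if the covariates explained 10% to 30% of within-brand variance and were balanced across brands (an assumption), 41% would rise to 45% to 57%, and by less if they differ by brand.

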#### ***B2a. Subject inclusion/exclusion criteria***

Adult ST users (18 years or older) who are interested in the study will telephone the research clinics, be informed about the study, and initially screened in order to determine whether they meet specific inclusion/exclusion criteria.

Inclusion criteria include:

- a) use of a consistent brand and daily amount of ST for the past 6 months;
- b) in good physical health (no unstable medical condition and no kidney or liver disease);
- c) stable, good mental health (e.g., no recent unstable or untreated psychiatric diagnosis, including substance abuse, as determined by the DSM-IV criteria).
- d) use of one of the following smokeless tobacco products:

(UPDATED BRANDS BY GROUP): 1) Camel Snus, Marlboro Snus; 2) Skoal Long Cut Mint, Skoal Fine Cut Original, Copenhagen Long Cut Original, Kodiak Wintergreen, Skoal Bandits Wintergreen, Skoal Pouches Straight, Skoal Pouches Wintergreen; 3) Grizzly Long Cut Straight, Skoal Long Cut Straight, Grizzly Long Cut Mint, Grizzly Long Cut Wintergreen, Grizzly Pouches Wintergreen, Skoal Pouches Mint, Kodiak Pouches Wintergreen; 4) Grizzly Fine Cut Regular; 8) Copenhagen Fine Cut Original, Copenhagen Long Cut Straight, Grizzly Pouches Straight, Skoal Long Cut Classic, Skoal Long Cut Wintergreen, and Dual Users of Camel and Marlboro Snus and cigarettes.

Exclusion criteria include:

- a) currently using other tobacco (>1 episode of smoking per week on average; no combustible tobacco use in the last 21 days and CO >8 ppm) or nicotine products;
- b) female subjects pregnant or nursing;
- c) use of alcohol within the last 24 hours of testing and no more than 21 drinks per week at phone screening;
- d) use of any inhalable drugs in the last 14 days and regular use >1 times per week;
- e) current infection or use of antibiotics;
- f) active liver or kidney disease, or UTI which would interfere with biomarker measures.

Subjects meeting these criteria will then be asked to come into the research clinic for an orientation visit, to provide informed consent, and to engage in more thorough screening. Subjects will also be required to complete a tobacco use questionnaire, medical history form (which will be reviewed by a physician), and baseline measurements (see below).

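### Aim 1 analyses six brands, but Table 2 holds 24 products in six groups: the one-way ANOVA has no product term, so its result covers only the product mix enrolled and its 5% level does not carry over to claims about nicotine or TSNA class

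*Combined protocol and SAP*

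**What the plan says.** Section C1, Primary Aim 1, plans one global test for each biomarker: "The one-way analysis of variance (ANOVA) will be used to compare the mean toxicant levels between all six brands". If it is significant, Tukey comparisons follow at 5% overall, and a geometric mean with a 95% interval is given for each brand.

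Section C2 sizes the study on the same unit: "The goal is to enroll 100 subjects for each of the six brands listed in Table 2". It adds that "this F-test will have 92% power to detect a significant difference at the 0.05 level". The condition attached is a gap of 0.5 SD or more between the highest and lowest of the six means. On the error term it says: "This is the common SD and is equivalent to the root of the Mean Square Error (MSE) from the one-way ANOVA".

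Secondary Aim 4 in C1 weights the six means from this ANOVA by market share.

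Table 2 in B2d does not list six brands. It has 24 product rows in groups numbered 1, 2, 3, 4, 6 and 8, each defined by a nicotine class and a TSNA class. Group 4 is a single product, "Grizzly Fine Cut Regular". The eligibility list in B2a also works by group and puts seven products in one of them: "2) Skoal Long Cut Mint, Skoal Fine Cut Original, Copenhagen Long Cut Original, Kodiak Wintergreen, Skoal Bandits Wintergreen, Skoal Pouches Straight, Skoal Pouches Wintergreen". It has no Group 6, adds dual users of snus and cigarettes, and places some products in different groups from Table 2.

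No section includes a product-within-group term, says whether products are fixed or random, sets product quotas within a group, or gives a between-product variance for any biomarker.

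**The concern.** Users of one product share that product's constituents, so their biomarker values may be alike for reasons unrelated to the group's class. Products within a group can differ widely: in Group 8 of Table 2, nicotine runs from 0.48 to 2.88 mg/g, a sixfold range (2.88 / 0.48 = 6). C2 itself expects mean uptake to differ between brands.

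A one-way ANOVA on groups takes in these product differences, but it treats them as 100 independent pieces of user noise per group. For a statement about a nicotine or TSNA class, the replicate is the product, and a group has only 1 to 7 of them. A difference driven by one product could then be reported as a class effect, with an interval that is too narrow for that claim.

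The Aim 4 burden estimate is also affected. Within each group, the mean it weights reflects who enrolled, not what sells.

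**Working it through.** **Inputs.** From C1 and C2: six groups, 100 users each, alpha 0.05, range of means 0.5 SD, stated power 92%. From Table 2, grouped by the nicotine cut-points printed beneath it and the TSNA cut-points in the B2d text: 4, 7, 5, 1, 2 and 5 products in Groups 1, 2, 3, 4, 6 and 8 (total 24). Assumed, because the documents give no value: the product ICC, meaning the share of within-group biomarker variance that lies between products.

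**1. The plan's own figure.** The noncentrality is lambda = 100 x (sum of squared deviations of the group means, in SD units), with 5 and 594 df.
- Six equally spaced means over 0.5 SD: deviations ±0.25, ±0.15, ±0.05; sum of squares 2 x (0.0625 + 0.0225 + 0.0025) = 0.175; lambda = 17.5; power 91.6%. This reproduces the 92%.
- Only the two extreme means differ from the middle: 2 x 0.0625 = 0.125; lambda = 12.5; power 78.4%.

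The 92% therefore assumes equally spaced (or more favourable) means, independent users and no product variance.

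**2. What the ANOVA does with product variance.** Set the total variance to 1. With s equally used products regarded as random, the variance of a group mean is ICC/s + (1 - ICC)/100. The ANOVA uses about 1/100. At ICC 0.03 and five products, the ratio of standard errors is sqrt(0.03/5 + 0.97/100) / 0.1 = sqrt(0.0157) / 0.1 = 1.25.

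**3. Rejection rate with no true group difference.** Simulation of the planned F-test, 20,000 runs per setting, Table 2 group sizes. Results agree to within about one percentage point between repeated sets of runs.

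| Assumed ICC | Products random, equal use | Products random, half of each group on one product |
|---|---|---|
| 0 | 5% | 5% |
| 0.01 | 16% | 18% |
| 0.02 | 28% | 33% |
| 0.05 | 55% | 63% |
| 0.10 | 77% | 85% |

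Alternative group sizes, including those of the eligibility list, give 14% to 16% at ICC 0.01 and 71% to 80% at 0.10 under equal use. The discrepancy between the two lists does not drive the result.

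With fixed products and equal means for the enrolled mixes, the same test rejects in 3% to 5%.

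**4. Is the ICC range plausible?** The pooled within-group SD of the log constituent in Table 2 is about 0.42 for nicotine and 0.21 for NNK+NNN. Suppose log uptake moves with log content at slope b, and users of one product have log SD sigma. Then ICC = b²·SD² / (b²·SD² + sigma²). Assuming b of 0.5 or 1 and sigma of 0.6 to 1.2:
- lowest: 0.25 x 0.21² / (0.25 x 0.21² + 1.44), about 0.01;
- highest: 0.42² / (0.42² + 0.36), about 0.33.

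Small non-zero values are credible, but this rests on assumed slopes and SDs.

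**5. Power for a class-level test.** In a balanced layout of six groups by four products, the group effect is tested against products within group on 5 and 18 df, with lambda = 0.175 / (ICC/4 + (1 - ICC)/100).
- ICC 0: lambda = 17.5; power 81%.
- ICC 0.01: 0.175 / 0.0124 = 14.1; power 70%.
- ICC 0.02: 0.175 / 0.0148 = 11.8; power 61%.
- ICC 0.05: 0.175 / 0.0220 = 8.0; power 43%.

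With the real, unequal group sizes, a plain ratio of the group to the product mean square still rejects in 7% to 21% of null studies at ICC 0.01 to 0.20 under equal use. A class-level test therefore needs a mixed model with suitable degrees of freedom.

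**The case against.** The strongest reply is that the products are not a random sample of anything. B2d says they were chosen for market share and for a range of constituent levels, Aim 1 concerns marketed products, and Aim 4 weights by their market share. On that reading products are fixed and the F-test keeps its level. C1 also leaves the link to constituent level mainly to Aim 2, which correlates each biomarker with the matching product constituent, so Aim 1 need not be read as a class comparison.

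Much of this stands, and it rules out two stronger readings. A reader might infer that product variation is missing from the error term. It is not: it sits in the within-group mean square, and the fault lies in what it is averaged over. A reader might also infer that false group differences will be declared far too often whatever is claimed. The documents do not support that. The inflation requires products to stand for their class and a non-zero ICC, and the documents state neither.

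The reply does not rescue the wording of C1. The groups are built on nicotine and TSNA class, so a class reading invites itself. With fixed products each geometric mean still describes an uncontrolled mix, because no product quotas are set. The market weights in Aim 4 still do not reach the products inside a group.

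Some of the differences between Table 2 and the eligibility list in product placement may come from PDF extraction. The absence of Group 6 from B2a does not depend on row alignment.

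**Conclusion.** The point holds in conditional form. It needs no assumption to see that C1 and C2 are written for six brands while Table 2 holds 24 products in six groups, and that no product term is planned.

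What follows depends on the claim made. For the named products in the mix enrolled, the test is valid or slightly conservative, but its result does not describe a nicotine or TSNA class. For a class-level claim with products random, the nominal 5% does not hold at any of the non-zero ICCs tested, and the 92% power does not apply. Those sizes rest on an ICC the documents do not give.

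Group 4 is a limit under any model: with one product, class and product cannot be separated.

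**What to change.** **In C1 (Aims 1 and 4):**
- Replace six brands by six product groups, and reconcile the groups in B2a with those in Table 2.
- Report geometric means and 95% intervals by product.
- Add product nested in group to the model and report the test of products within group.
- Limit the group comparison to the named products enrolled. Base any claim about nicotine or TSNA class on a mixed model with product as a random effect and small-sample degrees of freedom (for example Kenward-Roger).
- Apply the Aim 4 market shares to product-level means.
- State that Group 4 describes one product.

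**In C2:** state that 92% assumes independent users, equally spaced means and no product variance, and that power for a class-level comparison is lower, with the assumed ICCs shown.

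**Cost:** revised wording and one extra model term. The brand used is already recorded in the tobacco use history, so no new data are needed. The price is wider intervals and lower power for class-level claims. For that reason, making the random-effect model the only primary test would be a debatable trade.
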